## 9.2. Sample Size Determination

The primary endpoint is Objective tumor response assessed by RECIST version 1.1 per ICR. Analysis of tumor response will be based on both Overall tumor response and on Intra-Cranial tumor response.

OR is defined as a confirmed CR or confirmed PR from the first dose of study treatment until disease progression, start of anticancer therapy or death due to any cause. Both CR and PR must be confirmed by repeat assessments performed no less than 4 weeks after the criteria for response are first met.

ORR is defined as the proportion of treated participants with confirmed CR or confirmed PR per ICR assessment and will be estimated together with its 2-sided exact 95% CI (using an exact Clopper-Pearson CI).

According to literature, platinum-based doublet chemotherapy in patients with ALK + NSCLC refractory to second generation TKIs has an objective response rate of approximately 30%. Setting as target for lorlatinib a response rate of about 43% (as observed in cohort EXP-3B of phase 2 portion of study B7461001), a sample size of 60 participants would result in an exact two-sided 95% CI of the ORR with lower limit of the CI greater than 30%. In order to compensate for a potential 15% drop out rate (participants with death prior to first post-baseline assessment, inadequate baseline assessment, new anticancer therapy started prior to first post-baseline assessment, post-baseline disease assessments missing), the overall sample size for the study is set to 70 participants.

The study will be considered to have met its primary endpoint if the lower limit of the 95% confidence interval around the estimated ORR excludes 30%.

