	• Using the Kaplan-Meier method, estimate its associated statistics on TTP (including the median TTP with two-sided 95% CI, the TTP rates at clinically meaningful timepoints with two-sided 95% CI) for all participants who received at least one dose of lorlatinib without regard to discontinuation from treatment unless death occurs, new anti-cancer therapy is initiated or extended gap in tumor assessment is present prior to progression. TTP is defined as the time from date of first dose to the date of the first documented PD.				
	This analysis is based on ITT population. Participants with an event more than 12 weeks (24 weeks post the first 42 weeks) after the last adequate tumor assessment will be censored on the date of the last adequate tumor assessment prior to the gap that documented no progression. If the participant dies before progression, the participant will be censored on the date of death. If a new anticancer therapy starts prior to an event, the participant will be censored on the date of the last adequate tumor assessment that				

Endpoint	Statistical Analysis Methods				
	documented no progression prior to start of the new anti-cancer therapy. Participants with inadequate baseline assessment or with a adequate post-baseline tumor assessments within 12 weeks after the start date will be censored on the start date, unless the participant dies within 12 weeks of the start date, in which case, the patient who be censored on date of death. The CI for the median TTP will be calculated according to Brookmeyer and Crowley method, and the CIs for the survival function estimates at the timepoints will be derived using the log(-log) method.				
	PFS by ICR/INV				
	• Using the Kaplan-Meier method, estimate its associated statistics of PFS (including the median PFS with two-sided 95% CI, the PFS rates at clinically meaningful timepoints with two-sided 95% CI) for all participants who received at least one dose of lorlatinib without regard to discontinuation from treatment unless new anti-cancer therapy is initiated or an extended gap in tumor assessment is present prior to progression or death. PFS is defined as the time from date of first dose to the date of the first documented PD or death due to any cause, whichever occurs first.				

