5.1. Hypotheses and Decision Rules

5.1.1. Hypotheses and Sample Size

According to literature, platinum-based doublet chemotherapy in participants with ALK + NSCLC refractory to second generation TKIs has an objective response rate of approximately 30%. Setting as target for lorlatinib a response rate of about 43% (as observed in cohort EXP-3B of phase 2 portion of study B7461001), a sample size of 60 participants would result in an exact two-sided 95% CI of the ORR with lower limit of the CI greater than 30%. In order to compensate for a potential 15% drop out rate (participants with death prior to first post-baseline assessment, inadequate baseline assessment, new anti-cancer therapy started prior to first post-baseline assessment, post-baseline disease assessments missing), the overall sample size for the study is set to 70 participants.

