5.2.15. Analyses for Time-to-Event Endpoints

Time to event endpoints will be summarized using the Kaplan-Meier method and estimated survival curves will be displayed graphically when appropriate. Graphs will describe the number of participants at risk over time. The median, quartiles, and probabilities of an event at particular points in time will be estimated by the Kaplan-Meier method. Confidence intervals for medians and quartiles are based on the Brookmeyer-Crowley method. Confidence intervals for the estimated probability of event at a particular timepoint will be generated using the log(-log) method with back transformation to a confidence interval on the untransformed scale. Summaries of the number and percentages of participants with an event will also be provided on summary tables and figures.

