The censoring and event date options to be considered for the TTP analysis are presented in Table 4.

Scenario	Date of event/censoring	Outcome
No adequate baseline assessment	date of first dose	Censored
Progression \leq 98 days after last adequate tumor assessment or \leq 98 days after date of first dose	Date of progression	Event
Death \leq 98 days after last adequate tumor assessment or \leq 98 days after date of first dose	Date of death	Censored
Progression or death > 98 days after the last adequate tumor assessment ^a	Date of last adequate assessment ^b documenting no	Censored
No progression	PD prior to anti-cancer therapy or missed assessments	
New anti-cancer therapy given prior to PD	therapy of missed assessments	

 Table 4.
 Outcome and event dates for TTP analyses

^a if there are no adequate post-baseline assessments prior to PD or death, then the time without adequate assessment should be measured from the date of first dose; if the criteria were met the censoring will be on the start date.

Summaries used for reporting:

Kaplan-Meier estimates (product-limit estimates) will be presented together with a summary of associated statistics including the median TTP time with two-sided 95% CIs. The TTP rate at 12 months will be estimated with corresponding two-sided 95% CIs. The CIs for the median will be calculated according to Brookmeyer and Crowley and the CIs for the survival function estimates at the timepoints defined above will be derived using the log(-log) method according to Kalbfleisch and Prentice (conftype=loglog default option in SAS Proc LIFETEST). The estimate of the standard error will be computed using Greenwood's formula.

Frequency (number and percentage) of participants with PD and each censoring reasons will be presented along with the overall event and censor rates.

Reasons for censoring will be summarized according to the categories in Table 5. If a participant meets multiple definitions for censoring the list will be used to define the hierarchy.

Hierarchy	Condition	Censoring Reason
1	No adequate baseline assessment	No adequate baseline assessment
2	Start of new anti-cancer therapy before event.	Start of new anti-cancer therapy
3	Event more than 98 days from last adequate post-baseline tumor assessment/start date	Event after missing assessments ^a
4	No event and withdrawal of consent date ≥ start date OR End of study (EOS) = Subject refused further follow-up	Withdrawal of consent

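### The 12-month TTP rate is a Kaplan-Meier estimate with deaths censored, so it is not the share of treated participants with documented progression; a cumulative incidence should be reported beside it

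*SAP*

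**What the plan says.** - **Event and censoring.** SAP 3.2.8 and 6.2.8 define TTP from first dose to first documented PD. Death is not part of the event. Protocol 9.4.1 says: "If the participant dies before progression, the participant will be censored on the date of death". SAP Table 4 agrees for a death within 98 days of the last adequate assessment or of first dose. A death later than that is censored at the last adequate assessment.
- **Estimator.** SAP 5.2.15, which covers all time-to-event endpoints, says: "The median, quartiles, and probabilities of an event at particular points in time will be estimated by the Kaplan-Meier method". For TTP, SAP 6.2.8 adds: "The TTP rate at 12 months will be estimated with corresponding two-sided 95% CIs". It places the log(-log) interval on the survival function. Neither document names a cumulative-incidence or competing-risk estimate.
- **Estimand.** Protocol 9.1.1 and the objectives table in SAP 2.1 list death among the events that end follow-up for TTP. The four-attribute TTP estimand in SAP 2.1.2 lists only new anti-cancer therapy and an extended assessment gap as intercurrent events, and gives the KM median as its summary.
- **Internal conflict.** The third censoring bullet of SAP 6.2.8 concerns participants with no adequate baseline assessment or no post-baseline assessment. For them it counts a death by day 98 as a TTP event. Table 4 and protocol 9.4.1 censor that death.
- **Reported alongside.** The SAP also plans 12-month PFS (death counted), the PFS events split into PD and death, and a table of TTP censoring reasons that includes death.

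**The concern.** Death before PD is not ordinary loss to follow-up, because it rules the TTP event out. KM treats a censored participant as still able to progress and gives that person the later progression experience of those still under observation. With deaths censored, 1-KM therefore describes a setting in which nobody dies first. It is not the proportion of treated participants who progressed. SAP 5.2.15 nevertheless calls the KM quantity the probability of an event at a given time, and a reader will naturally take that as an absolute risk.

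TTP is to be reported by ICR and by INV in a study the EMA requested for more efficacy data. The shift is systematic and goes one way only. The issue is specific to TTP, because PFS, DoR and IC-DoR count death as an event.

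**Working it through.** **Inputs.** The TTP set is the ITT population. On its size the SAP says that "the overall sample size for the study is set to 70 participants". The documents give no expected 12-month TTP, PFS or number of deaths before PD, so those are assumptions below.

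**The plan's own figure.** The only stated calculation is the sample size. With 26/60 = 43.3% responding, the exact 95% CI is 30.6% to 56.8%, so its lower limit is above 30% as stated. Allowing for 15% loss, 60/0.85 = 70.6, close to the planned 70. There is no TTP figure to reproduce, so this only fixes N = 70.

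**Excess under constant hazards.** Let F be the true 12-month incidence of PD and D = d/70 the share who die before PD by month 12. Then

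1-KM(12) = 1 - (1 - F - D)^(F/(F + D)), and the excess is 1-KM(12) - F.

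Example with F = 50%, d = 4: D = 0.0571 and F/(F + D) = 0.8974, so 1-KM = 1 - 0.4429^0.8974 = 51.86%. The excess is 1.86 points.

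| True 12-month PD incidence | d = 1 | d = 4 | d = 5 |
|---|---|---|---|
| 30% | 0.24 | 1.01 | 1.27 |
| 40% | 0.34 | 1.41 | 1.78 |
| 50% | 0.44 | 1.86 | 2.35 |
| 60% | 0.56 | 2.37 | 3.01 |
| 70% | 0.70 | 2.98 | 3.80 |
| 80% | 0.87 | 3.74 | 4.79 |

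(Percentage points, N = 70, no other censoring.)

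**Timing of deaths.** Take 35 PDs by month 12.
- If all deaths precede every PD, 1-KM = 35/(70 - d). The excess is 35/66 - 35/70 = 3.03 points for d = 4 and 35/65 - 35/70 = 3.85 points for d = 5.
- If all deaths follow the last PD, the excess is 0.

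**Simulation.** This used exponential TTP with assumed medians of 5.6 to 14 months and deaths either in months 0 to 3 or spread over months 0 to 12. Four to five deaths gave an excess of 1.5 to 5.2 points, and one death gave 0.4 to 1.0.

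**Scale against sampling error.** The approximate 95% half-width is 1.96 x sqrt(F(1 - F)/70). This is 11.7 points at F = 50% and 10.7 at 30% or 70%. At 80% it is 1.96 x sqrt(0.80 x 0.20/70) = 9.4.

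**Sensitivity to the assumed median.** Write lambda = ln2/median PFS and s for the share of PFS events that are deaths without PD. Then 1-KM = 1 - exp(-(1 - s) x lambda x 12), and the incidence of PD is (1 - s) x (1 - exp(-lambda x 12)).
- Median 5.6 months, s = 8% (4.3 deaths by month 12): 74.5% against 71.2%, an excess of 3.3 points or 0.62 SE.
- Median 10 months, s = 10% (about 4 deaths): 52.7% against 50.8%, an excess of 1.9 points or 0.31 SE.

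**The case against.** The strongest case on the other side has four parts.

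1. **Death censoring is prespecified.** Protocol 9.1.1 and the SAP 2.1 table say that TTP follow-up ends at death, and SAP 2.1.2 names the KM median as the summary. Nowhere does the plan call 1-KM the proportion progressed. This stands in large part, and is why the KM analysis should be kept. It does not cover the 12-month rate fully: the four-attribute estimand gives death no strategy, and SAP 5.2.15 describes the KM output as an event probability.
2. **The direction depends on the scale reported.** The interval in SAP 6.2.8 is on the survival function, so the rate may be S(12). A reader might infer that the reported number must overstate progression. The text does not settle that. If S(12) is reported, the same gap appears as too low a share without documented PD.
3. **Other outputs help.** PFS and the censoring table show much of what is needed. This holds in part. PFS does not isolate progression. In Table 5 the category for death ranks seventh, below the sixth-ranked category for no adequate post-baseline assessment, so deaths before the first scan can be tabulated elsewhere.
4. **The effect is modest.** TTP is descriptive, has no test, and the excess is well inside the confidence interval. This stands, and makes the change an improvement rather than a correction on which the study's conclusion depends.

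**Conclusion.** The point holds as a limit on what the 12-month TTP rate can be used to say. Any death that precedes a later PD makes 1-KM exceed the proportion with documented PD. Four to five such deaths in 70 give about 1 to 5 points if the 12-month PD incidence is 30% to 80%. This rests on assumed incidence and numbers of deaths, constant hazards and no other informative censoring. If all deaths came after the last PD, there would be no excess.

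Three stronger readings are tempting, and the documents do not support them.
- **A threshold at 4 to 5 deaths.** The excess starts with the first death that precedes a later PD and grows smoothly. A cut-off needs a tolerance, such as half a standard error, that the plan does not state. It also needs a short median. The 5.6 months in protocol 2.2 is a median duration of response in responders, not a PFS or TTP from first dose.
- **A magnitude taken from the drop-out allowance.** Protocol 9.2 reads: "In order to compensate for a potential 15% drop out rate (participants with death prior to first post-baseline assessment, inadequate baseline assessment", and goes on to further categories without splitting the 15%. Deaths before the first scan are also the ones the SAP 6.2.8 text may count as events, in which case they are not censored and add no such excess.
- **A threat to the main result.** The success rule in SAP 5.1.2 concerns ORR only and is unaffected.

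**What to change.** 1. First reconcile the SAP 6.2.8 bullet that makes some deaths by day 98 TTP events with Table 4 and protocol 9.4.1, so that each death has one status.
2. In SAP 6.2.8, with a matching line in 5.2.15, add the 12-month cumulative incidence of PD (Aalen-Johansen) with its 95% CI, by ICR and by INV. Treat death before PD as a competing event where Table 4 now censors at the date of death. Leave the other Table 4 rules (new therapy, gap over 98 days) unchanged.
3. Keep the prespecified KM median and curve, labelled as having deaths censored, and say whether the 12-month KM figure is S(12) or 1-S(12). Use the cumulative incidence for any statement about the proportion who progressed.

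The cost is a few lines of SAP text and one more analysis on the same data. The downside is that a cumulative incidence is less directly comparable with KM-based TTP from earlier studies, which is a further reason to keep the KM display. Deaths after a gap of more than 98 days would still be censored at the last adequate assessment, so the new estimate removes the problem only for deaths now censored at the date of death.

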6.3. Other Endpoint(s)

Not Applicable

6.4. Subset Analyses

Primary endpoint OR by ICR will be reported also by:

- prior ALK inhibitor (Alectinib or Ceritinib)
- prior Chemotherapy (Yes/No)

6.5. Baseline and Other Summaries and Analyses

6.5.1. Baseline Summaries

• Demographic and Physical Characteristics

The following demographic and baseline characteristics will be summarized by number and percentage:

- Gender(male, female)
- Age (18-<45; 45- <65; ≥65).

```
DMB02-GSOP-RF02 4.0 Statistical Analysis Plan Template 01-Nov-2018
PFIZER CONFIDENTIAL
Page 32
TMF Doc ID: 98.03
```

- Race (white, black, Asian, other)
- Eastern Cooperative Oncology Group (ECOG) Performance status

will be summarized by category (number and percent).

Age (continuous), weight (kg), will be summarized with descriptive statistics (mean, median, standard deviation, minimum, and maximum, inter quartile range).

• Disease Characteristics

The following baseline disease characteristics will be summarized by number and percentage according to both ICR/INV:

- Measurable disease at baseline (yes/no) (see section 5.2.5)
- Involved tumor sites at baseline.
- Number of sites of disease at baseline $(1, 2, \ge 3)$

Time since diagnosis (months), defined as (date of first dose – date of diagnosis)/30.4375, will be summarized by descriptive statistics (mean, median, standard deviation, minimum, and maximum).

Involved tumor sites at baseline will be derived from target and non-target lesions at baseline. Each participant will be counted once per organ. Similarly, number of sites of disease at baseline will be derived by counting the number of unique organ sites from target and non-target lesions at baseline. "Other" will be counted as one organ site.

Medical History

Medical history will be coded using the most current version of MedDRA and summarized by MedDRA's System Organ Class (SOC) and PT. Each participant will be counted only once within each PT or SOC. Summaries will be ordered by primary SOC and PT in descending order of frequency. Separate summaries will be provided for past and present conditions.

• Prior Anti-Cancer Treatments

Prior anti-cancer treatments include systemic therapy, radiation, and surgery. The number and percentage of participants in each of the following anti-cancer therapy categories will be tabulated:

- Participants with at least one type of prior anti-cancer treatment;
- Participants with at least one prior anti-cancer drug therapy;

- Participants with at least one prior anti-cancer radiotherapy;
- Participants with at least one prior anti-cancer surgery.

Prior anti-cancer drug therapy will be summarized as follows based on the number and percentage of participants:

- Number of prior anti-cancer therapy regimens: missing / 1 / 2 / 3 / ≥4;
- Number of participants who received prior chemotherapy
- Number of participants who received Alectinib/Ceritinib as Prior ALK Inhibitor

The prior anti-cancer drugs will be coded in the WHO Drug coding dictionary.

6.5.2. Study Conduct and Participant Disposition

The study protocol consists of two different epochs: Study and Treatment.

6.5.2.1. Participant Disposition

A summary of the number of participants enrolled by country and site will be provided for the Enrolled population.

Discontinuations from study will be summarized using the Enrolled set. Discontinuations from study treatment will be summarized using the ITT set

Discontinuations from study treatment due to adverse events will be identified as either related or not related to study treatment. If causality is missing the event will be considered related to treatment. If multiple events lead to study treatment discontinuation and at least one was considered related, discontinuation will be reported as related to study treatment.

An additional summary to meet European Union Disclosure requirements will categorize discontinuations due to adverse events based on the following categories:

- Adverse Event, not serious
- Adverse event, serious non-fatal
- Adverse event, serious fatal

6.5.2.2. Protocol Deviations

Protocol deviations will be compiled prior to database closure and will be summarized by category (n(%)) for the Enrolled Analysis Set. Categories will be assigned by the study Clinician.

6.5.3. Study Treatment Exposure

6.5.3.1. Exposure to lorlatinib

Exposure will be summarized for the ITT/Safety analysis set.

The summary of treatment exposure for lorlatinib will include the following information:

- Treatment duration (days)
- Cumulative dose (mg)
- Dose intensity (mg/day)
- Relative dose intensity (%).

The duration of lorlatinib (in days) is defined as:

Treatment duration (days) = (last dose date - first dose date + 1)

The cumulative dose (mg) of lorlatinib is the sum of the actual dose levels that the participant received (i.e., total dose administered (mg)).

The dose intensity (DI) and the relative dose intensity (RDI) of lorlatinib will be calculated for each participant during the study. The DI (mg/day) of lorlatinib during the study is defined as

DI (mg/day) = [cumulative dose (mg)]/[treatment duration (days)]

The RDI of lorlatinib is defined as the ratio of the DI and planned dose intensity d and expressed in %

RDI (%) = $100 \times [DI (mg/day]/[d (mg/day)].$

6.5.3.2. Dose Reductions and Interruptions

A dose reduction is defined as a non-zero dose that is less than the prior dose.

The number and percentage of participants with at least one dose reduction as well as a breakdown of dose reductions $(1 / 2 / 3 / \ge 4)$ will be summarized.

Reasons for dose reductions will also be summarized. Participants can contribute to more than one reason if multiple dose reductions occurred for different reasons, but will only be counted once per reason. Percentages will be calculated based on the total number of participants in safety analysis set.

An interruption is defined a 0 mg dose administered on one or more days. (Note: A dose interruption is not considered a dose reduction). The number and percentage of participants

DMB02-GSOP-RF02 4.0 Statistical Analysis Plan Template 01-Nov-2018 PFIZER CONFIDENTIAL Page 35 TMF Doc ID: 98.03 with dose interruptions and the corresponding reasons will be summarized. Participants can contribute to more than one reason if multiple dose interruptions occurred for different reasons, but will only be counted once per reason. Percentages will be calculated based on the total number of participants in safety analysis set.

What follows defines how dose interruptions will be counted in the case of multiple dose interruptions:

- If an interruption occurs consecutively for at least two days due to the same reason, then it will be counted only once.
- If an interruption occurs consecutively for at least two days due to different reasons, then it will be counted for each reason.
- If an interruption occurs for more than one day due to the same reason, but the days are not consecutive, i.e. there is at least one dosing day in between, then each dose interruption will be counted as a different occurrence.

